## 5.1 Subject Inclusion Criteria

All must be answered YES for the subject to be eligible for study participation:

- 1. Subject reads and signs the Informed Consent Form (ICF) and agree to have bronchoscopy with bronchoalveolar lavage under sedation or light anesthesia and comply with study procedures.
- 2. Healthy male or non-pregnant, non-lactating female subjects 18 to 45 years of age (both inclusive) at the time of dosing.
  - a. Note 1: Determined by medical history (MH), medication use, physical examination (PE), and vital signs, clinical laboratory tests and 12-lead ECG within reference ranges at Screening and Day-2. (See Sections 8.1 and 8.2, Appendix B, Table 2, Table 3 and Table 4 and the study-specific MOP.)

Exceptions to BP, HR and laboratory test values being with normal ranges are:

- Abnormal HR and BP on first measurement may be repeated twice more with the subject resting between measurements for at least 5 min according to Section 8.1.6.
- Subjects with baseline  $HR \ge 45$  to 50 bpm may be accepted if otherwise healthy adults with known history of asymptomatic bradycardia.
- Subjects with baseline SBP up to 140 mmHg and DBP up to 90 mmHg may be accepted if otherwise healthy.
- A laboratory value that is Grade 1 will be allowed if not considered to be clinically significant by the investigator, with the exception of ALT, AST, AP, BUN, urine protein, serum creatinine or estimated glomerular filtration rate (eGFR) <70 mL/min /1.73 m^2 by the Chronic Kidney Disease Epidemiology collaboration (CKD-EPI) equation.
- 3. Female subjects of childbearing potential should use highly effective methods of contraception from the time of screening to 30 days after dosing.
  - Note 1: A female is considered of childbearing potential unless post-menopausal (defined as history of ≥1 year of spontaneous amenorrhea and a FSH level >40 IU/L), or permanently surgically sterilized.

- Note 2: Highly effective contraceptive methods include: (a) surgical sterilization methods, such as tubal ligation, bilateral oophorectomy, salpingectomy, hysterectomy, or successful tubal obliteration (e.g., Essure®) with documented radiological confirmation test at least 90 days after the procedure, or (b) long-acting reversible contraception, such as progestin-releasing subdermal implants, copper intrauterine devices (IUDs), levonorgestrel-releasing IUDs.

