# 8.2.1 Clinical Laboratory Evaluations (Hematology, Coagulation, Chemistry, and Urinalysis).

Blood and urine samples for clinical laboratory tests will be collected at the Screening Visit and on Day -2 to determine eligibility, and on Day 1, pre-dose, to determine (Baseline). Clinical laboratory tests will also be collected on Day 2 ( $24 \text{ h} \pm 1 \text{ h}$  after dosing), Day 3 ( $48 \text{ h} \pm 1 \text{ h}$  after dosing), and on Day 14 ( $\pm 3 \text{ days}$ ) or ET. Subjects must be fasting at least for 6 h before any blood draw for clinical laboratory assessments. These tests will include:

- HEM: Hgb, Hct, RBC, platelet count, and WBC count with absolute differential count.
- COAG: INR with prothrombin time, alpha partial thromboplastin time.
- CHEM: electrolytes (sodium, potassium, chloride, total carbon dioxide [CO2]), calcium, magnesium, creatinine, with estimation of GFR by the CKD-EPI equation, blood urea nitrogen (BUN), glucose (fasting), total bilirubin, direct bilirubin, alanine aminotransferase (ALT), aspartate aminotransferase (AST), alkaline phosphatase (AP), total protein, albumin, TSH, free T4, and free T3.
  - The CKD-EPI equation, expressed as a single equation, is GFR = 141 × min(Scr/κ, 1)α × max(Scr/κ, 1)-1.209 × 0.993Age × 1.018 [if female] \_ 1.159 [if black], where Scr is serum creatinine, κ is 0.7 for females and 0.9 for males, α is
     -0.329 for females and -0.411 for males, min indicates the minimum of Scr/κ or 1, and max indicates the maximum of Scr/κ or 1 (Levey et al 2009).
- UA: Routine dipstick testing of clean-catch urine for blood, protein, and glucose
  - If urine dipstick is abnormal, urine microscopy will be performed.

Clinical laboratory tests at the Screening Visit and Day -2 should be in the normal reference range with exceptions. (See Section 5.2, Inclusion Criteria #2 and Appendix B, Table 3).

Laboratory values that are outside the range of eligibility but are thought to be due to an acute condition or due to collection or laboratory error may be repeated once, preferably within 24 h or as soon as subject is available.

Laboratory values will be transferred to Advantage eClinical®.

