#### 9.2.3 Procedures to be Followed in the Event of Abnormal Laboratory Test Values or Abnormal Clinical Findings

A licensed study clinician (listed on FDA Form 1572) will determine seriousness, severity, and causality of abnormal laboratory values; provide a medical evaluation of TEAEs; and classify TEAEs based upon medical judgment.

Abnormal laboratory values or clinical findings for all enrolled subjects after dosing will be assessed using the toxicity scales in Appendix B. Out of range values and findings noted at screening or baseline, but allowable for enrollment and dosing if within Grade 1, will only be considered TEAEs if their severity increases to Grade 2 or higher. For abnormalities noted from the time of study drug dosing, any Grade 1 or higher laboratory abnormality listed on the toxicity Table 3 in Appendix B will be entered in the database as a TEAE. Safety laboratory results that are reported as TEAEs will be evaluated by the CTU clinician as clinically significant (CS) or not clinically significant (NCS). Abnormal laboratory values, performed as part of HEM, COAG, CHEM, or UA but not listed in this toxicity table will be evaluated by the study clinicians, recorded in the source document and, if clinically significant, considered TEAEs and graded according to the criteria in Section 9.2.1.

Protocol-specific laboratory normal range values are included in the study-specific MOP and toxicity grades for evaluation of TEAEs are included in Appendix B, Table 3.

Gross blood in urine that is confirmed due to menses is not a TEAE (but is for all other reasons).

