- 10. The CKD-EPI equation, expressed as a single equation, is  $GFR = 141 \times min(Scr/\kappa, 1)\alpha \times max(Scr/\kappa, 1)-1.209 \times 0.993 Age \times 1.018$  [if female] \_ 1.159 [if black], where Scr is serum creatinine,  $\kappa$  is 0.7 for females and 0.9 for males,  $\alpha$  is -0.329 for females and -0.411 for males, min indicates the minimum of Scr/ $\kappa$  or 1, and max indicates the maximum of Scr/ $\kappa$  or 1 [Levey 2009].(Formula will be used and result will be included in the lab report)
- 11. Urinalysis (UA) by dipstick. If abnormal for blood, protein and glucose, perform microscopic UA. The results of microscopic UA supersede those of UA by dipstick. UA may be postponed in a menstruating female. Abnormal UA in a menstruating female is not graded as a TEAE; the UA should be completed after the end of menstruation.
- 12. Cystatin C in serum.
- 13. Kidney-injury molecule 1 (KIM-1) in urine.
- 14. Ear otoscopy, Valsalva test, tympanometry, stapedial reflexes, and pure-tone audiometry with standard frequencies and distortion product otoacoustic emissions (DPOAEs) at screening. Ear otoscopy, and pure-tone audiometry including high frequencies and DPOAEs at check-in (Day -2 [or Day -4 or Day -3 if needed]) and at Days 3 (+2 days), 14 (± 3 days), and 30 (± 4 days), or ET.
- 15. Subjects will be admitted to the ward on Day -2 after confirmation of eligibility.
- 16. Assignment to Lung PK timepoint cohorts (T1 T5) and Enrollment to be performed before 12-lead ECG on Day -1. Subjects with ECGs on Day-1 and pre-dose on Day 1 with clinically significant abnormalities according to the PI should not be eligible for receiving study drug and should be withdrawn and replaced.
- 17. Subjects may be discharged from the CTU after Day 3 collection of the 60-h plasma PK sample.
- 18. Duration of a ramycin infusion is  $30 \pm 5$  min.
- 19. Adverse events from the start of dosing to the end of the trial are considered treatment-emergent adverse events (TEAE) or serious AEs (SAE).

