#### Table 3: Toxicity Grading Tables – LABORATORY AEs
Laboratory AEs	Mild (Grade 1)	Moderate (Grade 2)	Severe (Grade 3)					
Urine								
URINALYSIS by Dipstick								
Protein	1+	2+	>2+					
Blood (occult)	1+	2+	>2+					
Glucose	1+	2+	>2+					
URINE MICROSCOPY								
Red blood cells (RBC) per HPF	3-10	11-30	>30 and/or gross blood					
White blood cells (WBC) per HPF	6-10	11-30	>30 and/or symptomatic urogenital infection					
Bacteria (microscopic)	few	moderate many						

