## Table 3: Toxicity Grading Tables – LABORATORY AEs

Note 1: With the exception of AST, ALT, AP, bilirubin, electrolytes, urine protein, BUN and creatinine, which should be within reference range, lab values of other analytes in the grade 1 range are acceptable for enrollment if (a) they are not considered to be clinically significant by the investigator and (b) there is no cluster of abnormal labs that combined are suggestive of an underlying disorder.

Note 2: Other Exceptions to screening laboratory tests' normal reference ranges are:

- a. Racially based low total WBC or neutrophil counts up to toxicity Grade 1 are allowed, but toxicity Grades 2 or 3 are exclusionary.
- b. Labs performed as part of a panel but not listed above are to be recorded in the database. If abnormal, they are not exclusionary and are not to be graded per Toxicity table, however, the investigator would make a clinical decision about their clinical significance and, if clinically significant, they will be graded according to the criteria in Section 9.2.1. (Examples include mean corpuscular volume (MCV), mean corpuscular hemoglobin (MCH), mean corpuscular hemoglobin concentration (MCHC), red cell distribution width (RDW), mean platelet volume (MPV), and nucleated red blood cell count (NRBC CT), which are included in a CBC with differential.)
- Note 3: If a subject was accepted into the trial with a laboratory value of an analyte that overlaps with values used for grading Grade 1 laboratory abnormalities, a TEAE will be reported if the on-study value of the same analyte increases to Grade 2 or higher.
- Note 4: If the dipstick UA is abnormal, a microscopic UA will be performed, and the results will supersede the results of the dipstick UA.
- Note 5: Menstruating females with a positive dipstick UA or microscopic UA may be retested following cessation of menses.
- Note 6: Isolated laboratory values that are outside the range of eligibility but are thought to be due to an acute condition or due to collection or laboratory error may be repeated once.

ECG interval abnormality	Reference range	Grade 1	Grade 2	Grade 3
QTcF interval prolonged (msec): • Male • Female	•_≤ 450 msec • ≤ 470 msec	Asymptomatic, QTcF • 451 – 479 msec • 471 – 479 msec	Asymptomatic, QTcF 480-500 msec OR increase in interval 30- 59msec above baseline	Asymptomatic, QTcF >500 msec OR increase in interval ≥60 msec above baseline

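### The protocol and SAP carry conflicting rules on whether an abnormal urinalysis in a menstruating woman is graded as a TEAE

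*Protocol*

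**What the plan says.** Three rules on menses and urinalysis (UA) coexist.

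- **Schedule footnote 11** (protocol Appendix A, Table 1; same wording in SAP Table 2): "UA may be postponed in a menstruating female", and "Abnormal UA in a menstruating female is not graded as a TEAE; the UA should be completed after the end of menstruation". The exemption is not tied to any analyte, and the postponement has no time limit.
- **Protocol 9.2.3.** The general rule for post-dose results is that any "Grade 1 or higher laboratory abnormality listed on the toxicity Table 3 in Appendix B will be entered in the database as a TEAE". The only menses exemption is narrower: "Gross blood in urine that is confirmed due to menses is not a TEAE (but is for all other reasons"). Section 8.2.1 likewise says that post-dose laboratory abnormalities are graded against Appendix B.
- **Protocol Table 3, Note 5** (SAP Table 4, Note 6): "Menstruating females with a positive dipstick UA or microscopic UA may be retested following cessation of menses". This permits a retest and says nothing about withholding a grade.

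The test covers more than blood. Section 8.2.1 describes it as "UA: Routine dipstick testing of clean-catch urine for blood, protein, and glucose", with microscopy if the dipstick is abnormal. Table 3 grades dipstick protein, blood and glucose, and on microscopy red cells, bacteria and "White blood cells (WBC) per HPF". Post-dose UA is scheduled at 24 h, 48 h and Day 14.

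**The concern.** Site and statistician cannot follow all three passages at once. For a menstruating woman with a new non-blood abnormality at 24 h or 48 h, whether a TEAE exists depends on which passage the site reads.

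Two things follow. First, the TEAE tables depend on an unstated choice. Second, the laboratory halting criterion in protocol 9.5.1 needs at least two subjects with related TEAEs of Grade 2 or higher in the same HLGT that do not resolve within 48 hours. A finding that is never graded as a TEAE cannot count toward that threshold of two.

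Nephrotoxicity is a named concern: the protocol identifies the kidney as the main target organ in the repeat-dose animal studies and asks for special attention to signs of renal toxicity. Of the laboratory measures that bear on the kidney, BUN, creatinine and the urinalysis items have rows in Table 3; eGFR, cystatin C and KIM-1 do not.

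**Working it through.** **1. One finding under each passage.** Take a menstruating woman with no UA abnormality before dosing. At 48 h her dipstick is positive for blood. Microscopy follows and shows white cells in the 11 to 30 per field band, which is Grade 2 in protocol Table 3 (and within the 11 to 50 Grade 2 band of SAP Table 4).

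| Passage | TEAE? | Can it count toward the halting rule? |
|---|---|---|
| Footnote 11 | No, not graded | No |
| 9.2.3 general rule, menses exemption limited to gross blood | Yes, Grade 2 | Yes, if related and unresolved |
| Table 3 Note 5 | Silent on grading; retest optional | Depends on which of the other two applies |

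The same split applies to dipstick protein or glucose, subject to step 4. Section 9.2.3 speaks of gross blood, so it also leaves unclear whether menstrual dipstick blood or microscopic red cells are exempt. Footnote 11 would exempt both.

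**2. What happens in the SAP displays.**
- Sample taken: SAP 9.6 puts the result in Listing 12, in Table 26 as an abnormal result, and in Tables 45 to 48 by abnormality and toxicity grade. No menses exclusion is stated for any of these. Under footnote 11 the same result would be missing from the TEAE summaries (Tables 15 to 20).
- Sample postponed: SAP 6.1 uses as denominator the participants with an available result at that timepoint, so the woman leaves the 24 h or 48 h row. If the later sample is handled as unscheduled, SAP 9.6 counts it only in listings and in maximum post-baseline severity.

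**3. How many women could meet the conflict.** The documents give no figure, so this rests on assumptions: a 28-day cycle, menses lasting L days, and dosing independent of cycle phase. Menses overlap a two-day window (Day 2 and Day 3) with probability (L + 2 − 1)/28.

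- L = 4: 5/28 = 17.9%
- L = 5: 6/28 = 21.4%
- L = 6: 7/28 = 25.0%

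If 10 of the 20 participants were women (assumed), the expected number is 1.8 to 2.5. If half of them had no bleeding on contraception, it halves to about 0.9 to 1.3. With wider inputs (6 to 14 women, L = 3 to 7, no contraceptive amenorrhoea) the expected number runs from 6 × 4/28 = 0.9 to 14 × 8/28 = 4.0. The chance of at least one such woman runs from 1 − (24/28)^6 = 60% to 1 − (20/28)^14 = 99%.

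Under the 4 to 6 day assumption, menses present on Day 3 end by Day 3 + 6 − 1 = Day 8 at the latest. That is before the earliest Day 14 visit (Day 11), so a persistent abnormality could still be seen there. What a postponement can miss is a transient one.

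**4. A further ambiguity.** Footnote 11 and Table 3 Note 4 say that microscopy results replace the dipstick results. Microscopy has graded rows only for red cells, white cells and bacteria. Read literally, a dipstick protein or glucose grade could be displaced in any participant, menstruating or not. The white-cell example in step 1 does not depend on this point.

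**The case against.** The strongest reply is that the footnote is a sensible guard against contaminated samples, and that little is lost. Much of this stands, and it rules out several stronger readings.

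- **A reader might infer that these results are dropped and that the UA grade tables are biased low.** The documents do not support this for samples that are taken: the footnote withholds TEAE status, and the SAP displays in step 2 have no menses exclusion. A by-timepoint value is lost only if the sample is postponed, and postponement is optional.
- **A reader might infer that menses from Day -2 to Day 1 leaves no baseline or eligibility protein result.** Protocol 11.4.3.2 and SAP 3.3.3 take baseline as the last value before dosing, so the Screening result would serve. The footnote does not waive eligibility. Inclusion Criterion 2 still requires laboratory values in range at Screening and Day -2, and it allows Grade 1 values only "with the exception of ALT, AST, AP, BUN, urine protein, serum creatinine or estimated glomerular filtration rate". Section 5 grants no exemptions.
- **A reader might treat this as a renal-safety trial with its main signal removed.** The primary objective is pharmacokinetic and safety is secondary. The protocol summary names creatinine, eGFR, cystatin C and KIM-1 for nephrotoxicity. None of them has a menses exemption, and creatinine and eGFR are measured at both 24 h and 48 h.
- **The percentages could be read as TEAEs lost.** They count women menstruating. A TEAE is lost only if such a woman also has a new gradable abnormality, and the documents give no rate for that.

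What the reply does not answer is the contradiction. Concern about contamination explains an exemption for menstrual blood, which 9.2.3 already provides. It does not tell the site which rule governs protein, glucose or white cells.

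**Conclusion.** The plan is inconsistent as written, and the inconsistency changes which events are graded and counted. Footnote 11 in both documents exempts every UA abnormality in a menstruating woman, 9.2.3 exempts only confirmed menstrual gross blood, and the Table 3 note exempts nothing. The consequences are limited to TEAE status, any contribution to the laboratory halting rule, and the timed 24 h or 48 h value when a sample is postponed.

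About 18% to 25% of women would be exposed to the conflict under the assumed 28-day cycle and 4 to 6 days of menses, and fewer with contraceptive amenorrhoea. The effect on TEAE counts cannot be quantified from the documents. The textual conflict does not depend on these assumptions. It should be corrected, as a point of moderate to minor weight.

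**What to change.** Reconcile footnote 11 (protocol Table 1 and SAP Table 2) with protocol 9.2.3 and 8.2.1, Table 3 Note 5 and SAP Table 4 Note 6, so that a single rule applies throughout. That rule should:

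- state which analytes the menses exemption covers. Section 9.2.3 limits it to blood confirmed as menstrual; the text should also say whether dipstick blood and microscopic red cells fall within it;
- keep the scheduled 24 h and 48 h samples, with a menses flag in the data, and report any post-menses repeat as an additional unscheduled result rather than a replacement;
- say how the replacement of dipstick by microscopy applies to dipstick protein and glucose, which have no microscopy row;
- confirm in SAP 9.6 that Tables 26 and 45 to 48 and the TEAE tables follow the same rule.

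The cost is a few lines in each document and one flag variable. The downside is that a few mild findings due to contamination will be graded as TEAEs; the flag lets a reader identify them.
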